6.2.2 Blinding procedures

The field tests will be unblinded as the differences in some of the hardware styles make it impossible to blind. As stated in section 6.2.1 all subjects will wear the RMD in the first field test period and the IMD in the second field test period. However, the lab tests in which feedback and speech are tested will be single blinded. In order to maintain the blind, the hearing aids will be taken from the subjects before the lab testing begins. They will be placed in the sound booth and seated in the middle of the speaker array. The PI will then enter the booth with the hearing aids hidden in their hand. The PI will approach the subjects from behind and place the hearing aids on the test subjects' ears without allowing them to see which hearing aids they are wearing during each testing session. The differences can be seen but not felt once the hearing aids are in position on the ears. The tubing and dome that fit in the ear canal are the same for each IMD style and their comparator; therefore, they will all feel the same to the subjects. The statistician will create a list to randomise the order of the blinded test condition using A and B to define which hearing aid (RMD or IMD) should be used for each round of tests. The PI will follow this list.

6.2.3 Other methods of minimising bias

The RMD will be programmed to a standard first fit setting that will be consistent with the first fit setting of the IMD. They will wear the RMD for approximately 10 +/- 5 days with the standard fitting before returning to the clinic for the IMD fitting. The equivalent fitting will reduce bias that subjects may otherwise have due to the fitting and ensure that the only difference between the two hearing aids is the feedback system.

6.3 Unblinding Procedures (Code break)

The field test portion of the study is performed unblinded. The blinding for the lab tests will be based on an A/B assignment with a list created by the statistician. The list will be located in the ISF so that the PI has access and knows which assignment to use for each appointment.

7. STUDY POPULATION

The study will take place in the clinic at Bernafon AG in Bern. No other sites will be used for the testing. A plan of action due to low enrolment is not necessary as subjects are recruited from a Bernafon database containing sufficient hearing impaired, experienced hearing aid users from which to choose.

7.1 Eligibility criteria

Participants fulfilling all of the following inclusion criteria are eligible for the study:

- All classifications of hearing loss (sensorineural, conductive, mixed)
- If the hearing loss is conductive or mixed, it must be approved for amplification by a physician

- All shapes of hearing loss (flat, sloping, reverse slope, notch)
- Hearing loss severity ranging from mild to profound
- German speaking
- Current hearing aid user
- Both genders
- Ages 18 and older
- Ability and willingness to sign the consent form

The presence of any one of the following exclusion criteria will lead to exclusion of the participant:

- Contraindications for amplification
- Active ear disease
- Inability to follow the procedures of the study due to language problems, psychological disorders, dementia, or other cognitive problems
- A reduced mobility making them unable to attend weekly study appointments
- A reduced ability to describe auditory impressions and the usage of the hearing aids
- Uncooperative so that it is not possible to record a valid pure tone audiogram
- A strongly reduced dexterity
- Central hearing disorders
- Bernafon employees
- Family members of Bernafon employees

7.2 Recruitment and screening

Bernafon has its own database of test subjects that use the Bernafon clinic for updated fittings and general maintenance of their hearing aids. These test subjects do not consist of employees of Bernafon or family members of employees. The test subjects for the current study will be chosen from the internal subject database. Bernafon does not advertise as a method of recruiting participants. Participants are collected and added to the database by word of mouth. If a current person from the database knows of another person with hearing loss they may give them the contact information of an audiologist within Bernafon. The person can then contact Bernafon if they wish to have a hearing test and determine if they're eligible to participate in a study. They are given a diagnostic audiological exam to determine if they have a hearing loss and the severity. If there are any medical indications it is recommended that they see a physician and then return if there are no contra-indications for hearing aids. During the hearing exam and medical history discussion it is determined whether the person is cognitively able to act on their own behalf. Additionally, if the person comes alone or if they are accompanied will help to determine their level of independence. If there is a study that is ready to take place, then that will be explained at this time including an estimation of how much time/number of appointments would be required of them. If there is no immediate study planned, the normal study process will be explained to the subjects and they will be put on a waiting list. It is explained that the general compensation for their time is by means of a box of batteries and cleaning accessories.

7.3 Assignment to study groups

For the field tests the allocation is single group; therefore, all the test subjects will be assigned to the same group. The field test 1 will be with the RMD and the field test 2 with the IMD.

For the live feedback and speech tests in the lab, the assignment to the test condition order will be randomised by the statistician. The test condition order will be randomised using an A/B assignment. This will minimize bias created when one test condition is tested in the final or last position all the time.

7.4 Criteria for withdrawal / discontinuation of participants

Participants are allowed to withdraw from the study at any time and for any reason. They do not have to share the reasons with the investigator. They will be asked to return the IMD. If the decision to withdraw is made by the investigator, the PI will inform the subject in person that they are no longer needed for the study. Reasons for withdrawing a participant from the study could be for non-compliance during testing, unreliable responses, medical reasons such as an ear infection, or the study may need

to be stopped or postponed. Any data gathered from these subjects will be used for the current study. All data will remain encoded because results are only recorded using the identification code of the subject. There are normally at least five “back-up” test participants on the list to replace those that withdraw or are withdrawn. The “back-up” participants have already been screened and deemed to be appropriate for the study.

8. STUDY INTERVENTION

8.1 Identity of Investigational Products (medical device)

For all three phases the treatment will be approximately 10 days of use with the IMD during which they will not use the RMD. They will be fit with the RMD for the first 10 +/- 5 days field test and then switch to the IMD for the assigned period of 10 +/- 5 days.

There will be lab tests during which the participants will use the RMD and the IMD, for up to 1.5 hours at a time during testing in the clinic.

8.1.1 Experimental Intervention (medical device)

The investigation product (IMD) is a medical device. It is a new version of a Bernafon hearing device. The name is Mermaid 9 S BTE. An initial version of the Mermaid 9 BTE was released to the market in early 2017. The new Mermaid 9 S does not deviate from the current commercial product except for the implementation of an updated chip with a new feedback cancellation system. Three BTE styles will be used for the IMD as it is important to test the feedback system with various hearing losses and hardware. The styles include a miniRITE-T which is appropriate for mild to severe hearing losses, a miniRITE-T (RC) rechargeable which also fits mild to severe hearing losses but uses a rechargeable battery and should be tested to ensure that the strength of the charge does not affect the performance of the feedback system. Lastly a super power (SP) BTE that fits moderate to profound hearing losses will be tested. Increased output of gain is a primary cause of feedback; therefore, it is important to test a BTE style that is expected to generate high amounts of gain.

The BTE is fitted with the body of the device over the ear, and a dome or earmold inside of the ear canal. Performance of the IMD is expected to be the same or better than the RMD. They are non-invasive devices. The dome that is worn inside the ear canal is made from non-toxic plastic and the earmolds are made of non-toxic plastic with an acrylic coating. An illustration of the three IMD BTE styles is shown in Figure 1.

Figure 1. Mermaid 9 S BTEs from left: miniRITE-T, miniRITE-T (RC), and SP BTE.

8.1.2 Control Intervention (comparator medical device)

The Reference Medical Device (RMD) is the current Mermaid 9 BTE. It is a CE marked hearing aid that was released to the market in 2017. The intended purpose of both the IMD and the RMD is the same - to amplify sounds. The strength of the amplification is programmed according to the subject's individual hearing loss. There is no placebo treatment used as the study uses the accepted standard treatment for hearing loss as the control. The only differences between the RMD and IMD are the upgraded chip that is capable of running the new feedback cancellation system and the rechargeable BTE style that has been added to the portfolio. The RMD and the IMD will be programmed based on each participant's hearing loss. The amplification will be verified for the devices using the REM. The two RMD BTE styles are shown in Figure 2.

Figure 2. Mermaid 9 miniRITE-T (left) and Supremia SP BTE (right).

8.1.3 Packaging, Labelling and Supply (re-supply)

The IMD is labelled by printing the name of the device directly onto the device. There is an individual serial number that also printed on the device. The production batch can be tracked through this serial number. The hearing aids are shipped in a box with a label on the outside of the box that states the name of the product, the serial number, and a short description. Inside the box is a case that houses the hearing aids. The HCP removes the case from the box, and the case is generally given to the end user in which to place the hearing aids whenever they are not worn. The packaging and labelling are the same for the IMD and the RMD.

8.1.4 Storage Conditions

The IMD devices are shipped as soon as they are produced because they are custom devices which are made to order. Therefore, they are not stored on any shelves. The conditions in which they should be shipped and kept by the end user are described in the IFU. They should not be exposed to temperatures below -25° and not above 60° Celsius.

8.2 Administration of experimental and control interventions

8.2.1 Experimental Intervention

The IMD is worn over the ear with a dome or earmold anchored inside the ear canal. It is non-invasive. The amplification is prescribed based on the participant's hearing loss. The IMD will be worn by each participant for approximately 10 days to give the subjects enough time to wear the devices in different environments and make a comparison between the IMD and the RMD. Normal use of a hearing aid is 8-10 hours per day. The participants will wear the IMD for the same amount of time during the day that they wear the RMD. The hours of daily use will be controlled with a data logging feature in the software that programs the hearing aids.

The study procedure will use a single group assignment design in which the subjects will wear the IMD at the same time. As stated previously, the device is non-invasive and requires no surgical procedure.

The subjects themselves will place the device in their ears each morning and remove them each night for sleeping. The test subjects are experienced hearing aid users and will require minimal explanation and/or training to use the IMD. They will be given an Instructions for Use booklet that explains how to insert the device and provides further instructions concerning cleaning, battery changing, and warnings.

8.2.2 Control Intervention

The RMD is worn over the ear with a dome or earmold anchored inside the ear canal. The RMD is the current marketed device. Participants will use the RMD programmed for the current study for approximately 10 days and then switch to the IMD. They will compare the IMD to the RMD after the field test with the IMD. Normal use of a hearing device is 8-10 hours per day. They will wear the RMD and the IMD for the same amount of time per day during the field tests. The hours of daily use will be

controlled with a data logging feature in the software that programs the hearing aids.

The study procedure will use a single group assignment design. The subjects will have already worn the RMD during the first period and will then all wear the IMD at the same time during the second period. As stated previously, the device is non-invasive and requires no surgical procedure. The RMD device is placed over the ear and the dome or earmold is placed inside the ear canal.

The subjects themselves will place the device in their ears each morning and remove them each night for sleeping. The test subjects are experienced hearing aid users and will require minimal explanation and/or training to use the RMD. They will be given an Instructions for Use booklet that explains how to insert the device and provides further instructions concerning cleaning, battery changing, and warnings.

8.3 Dose / Device modifications

The IMD will provide the same amplification as the RMD; therefore, the subjects should not experience any significant negative differences that would make them want to discontinue use of the device. However, if a subject does report such differences, that can be improved with fine tuning, fine tuning can be made to improve the situation enough for the subject to continue with the study. If the subject requests to discontinue they can immediately remove the IMD from their ear and return to using their own BTEs. They will be asked to return the IMD to Bernafon AG, but their data will still be included in the results for the current study. All data will remain encoded because the results are only recorded using the identification code of the subject.

8.4 Compliance with study intervention

It is clearly explained to the subjects that during each specific period of intervention it is important to the study that they only wear the RMD and IMD. However, their own BTEs are left in their possession for safety reasons in the event that they choose to discontinue their participation in the trial or a problem arises with the test devices. For ethical purposes, the subjects must have a back-up solution for their hearing impairment.

The data logging feature of the software monitors the average number of hours that the devices are worn each day. Therefore, it will be noted if the RMD and IMD have not been worn a standard or expected amount of time.

8.5 Data Collection and Follow-up for withdrawn participants

Any data that is collected will be kept in the data management database. The data will remain encoded because results are only recorded using the identification code of the subject. The analysis and report will include a summarized section based on the data available from all recruited subjects and another section based on the data from the subjects that complete the entire protocol will be analysed. Withdrawn subjects will have the same follow-up as those subjects that complete the trial. As all subjects are taken from the Bernafon database, all participants, including those that withdraw, are welcome to return to the clinic for fine-tuning and maintenance as needed.

8.6 Trial specific preventive measures

The performance of a hearing aid is not impacted by medication. The subjects will continue to take whatever type of medication that they normally take. There will be no impact on the study objectives.

8.7 Concomitant Interventions (treatments)

Test subjects will continue to receive any concomitant care and medication that they normally receive during the trial. All test subjects will already be hearing aid users and will have, therefore, used them while receiving other types of care or medications. There will be no impact on the study objectives.

8.8 Medical Device Accountability

The RMD and IMD devices have serial numbers by which the individual device can be identified, and the production history traced. The devices will be shipped from the production lab in Poland. The serial numbers will provide traceability of their production. All devices undergo testing in production before being shipped. Only IMD that are from a tested batch will be used in the study.

8.9 Return or Destruction of Study Drug / Medical Device

At the end of the study all of the subjects will return the IMD to the site in Bern. It will be noted in the device accountability log and CRF that the devices were returned.

The PI will then return the devices to the Sponsor.

9. STUDY ASSESSMENTS

9.1 Study flow chart(s) / table of study procedures and assessments

The following tables outline the visits for each phase. The scheduled visits and the testing is the same for each phase. The only difference is the hardware style that will be tested.

Phase 1 (miniRITE-T)

Study Activity	Intervention Period		
	Screening/Visit 1	Visit 2	Visit 3
	Day 0	10 +/- 5 days	20 +/- 5 days
Patient Information and Consent	x		
Demographics	x		
Medical/Hearing History	x		
In-Exclusion Criteria	x		
Randomisation and blinding (of feedback tests)		x	
Randomisation and blinding (of speech tests)			x
Otoscopy	x	x	x
Audiometry	x		
Administer Medical Device	x	x	
REM	x	x	
Primary Variable (Live Feedback Test)		x	
Secondary Variables (Speech Testing)			x
Other Variables (SSQ Questionnaire)			x
Other Variables (Product Questionnaire)	x	x	
Preference Questionnaire			x
Adverse Events	x	x	x

Phase 2 (miniRITE-T rechargeable)

Study Activity	Intervention Period		
	Screening/Visit 1	Visit 2	Visit 3
	50 +/- 15 days	60 +/- 5 days	70 +/- 5 days
Patient Information and Consent	x		
Demographics	x		
Medical/Hearing History	x		
In-Exclusion Criteria	x		
Randomisation and blinding (of feedback tests)		x	
Randomisation and blinding (of speech tests)			x
Otoscopy	x	x	x
Audiometry	x		
Administer Medical Device	x	x	
REM	x	x	
Primary Variable (Live Feedback Test)		x	
Secondary Variables (Speech Testing)			x
Other Variables (SSQ Questionnaire)			x
Other Variables (Product Questionnaire)	x	x	
Preference Questionnaire			x
Adverse Events	x	x	x

Phase 3 (Super Power BTE)

Study Activity	Intervention Period		
	Screening/Visit 1	Visit 2	Visit 3
	180 +/- 30	190 +/- 5 days	200 +/- 5 days
Patient Information and Consent	x		
Demographics	x		
Medical/Hearing History	x		
In-Exclusion Criteria	x		
Randomisation and blinding (of feedback tests)		x	
Randomisation and blinding (of speech tests)			x
Otoscopy	x	x	x
Audiometry	x		
Administer Medical Device	x	x	
REM	x	x	
Primary Variable (Live Feedback Test)		x	
Secondary Variables (Speech Testing)			x
Other Variables (SSQ Questionnaire)			x
Other Variables (Product Questionnaire)	x	x	
Preference Questionnaire			x
Adverse Events	x	x	x

9.2 Assessments of outcomes

9.2.1 Assessment of primary outcome

The primary outcome is the live feedback testing results of the IMD compared with the RMD. The hearing aids will be programmed with the same gain and feedback elicited in simulated real-life situations that cause feedback including: Inserting and removing the hearing aids from the ears, holding a telephone up to the ear, sitting close to a wall, putting the hand up to the ear. The subjects will answer questions about the annoyance caused by the elicited feedback. The feedback test will be tested with the RMD and the IMD at the second appointment.

9.2.2 Assessment of secondary outcomes

Speech will be assessed using a standardized speech test (Wallenberg & Kollmeier's Rhyme Test (WaKo)) at the third appointment. Subjects will respond to the speech testing in an unaided condition and aided conditions with the RMD and the IMD. They will also complete product questionnaires with specific questions about feedback, sound quality, and unexpected behaviour. The questionnaires are given to them to take home on the first and second appointments. A standardized questionnaire (SSQ) that directly compares the IMD and RMD and a preference questionnaire will be completed at the third appointment.

9.2.3 Assessment of safety outcomes

Questions concerning unexpected events, sounds, and behaviour are included in the questionnaire that is given to the subjects to complete at home on the first and second appointments.

9.2.3.1 Adverse events

For the recording of adverse events the subjects will be asked for a description of the event including time/date of onset, how long it lasted, how many times it occurred, and if it caused discomfort or pain or a disruption of hearing ability. Before the end of each appointment, the subjects will be asked if they have experienced any adverse events. It will be explained that adverse events are not restricted to problems related to the hearing aids or their hearing but can include allergies, broken legs, headaches, etc. They will be recorded on the AE forms in the CRF.

9.2.3.2 Laboratory parameters

Not applicable

9.2.3.3 Vital signs

Not applicable

9.2.4 Assessments in participants who prematurely stop the study

After the study concludes the subjects will return the IMD. The follow-up procedure will be the same as for all active test subjects. They will be instructed to return to the clinic for any required maintenance or fine-tuning of their own devices. Those that prematurely withdraw from the study will still be wearing their own devices; therefore, their follow-up treatment will be the same as for the other participants that finish the study.

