11. STATISTICAL METHODS

11.1 Hypothesis

The feedback canceller used in the IMD is an extension of the feedback canceller implemented in the RMD but newly designed for dynamic situations, e.g. insertion of the device, phone call, removal... Regarding feedback performances, we can expect less annoyance of feedback in some dynamic situations which are tested within the live feedback test. The feedback canceller in static situations is based on the same principle and functions the same in the IMD as in the RMD.

Variance in the results can come from manipulation, individual programmed gain, acoustical coupling within the ear canal, or individual rating. However, there are no technical reasons that feedback annoyance with IMD should be higher than with the RMD. Therefore, a one-sided test will be used to evaluate the benefit of the IMD in terms of feedback annoyance.

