11.2 Determination of Sample Size

The primary outcome, the live feedback test, measures the feedback annoyance on a visual analogue scale for different manipulations that could produce feedback. An internal pilot test found an average improvement of 1.54 points (SD 1.63 points) with the newly developed feedback canceller (prototype) on the feedback annoyance scale. This effect was obtained on a group of listeners with moderate to severe hearing loss.

A test with a homogenous group of participants, i.e. hearing loss and hearing aid style, and repeated measures would require 11 subjects to show an effect with an alpha value of 2.5%, a power of 80%, and an effect size of 0.94. Similar conditions can be found in subjects who are eligible to be fitted with the Super Power BTE device. Therefore, 11 participants should be recruited for the third phase.

For the first and second phases, the inclusion criteria for the hearing loss degree covers a larger range of configurations. The IMD styles, i.e. miniRITE-T and miniRITE-T rechargeable, offer also more acoustical options than the SP style during the fitting. These 2 parameters, the hearing loss degree and acoustical coupling, are known to influence the risk of acoustical feedback. This added variation might reduce the effect size of the feedback annoyance with the IMD and must be compensated with an increased sample size. For the first and second phases, we propose to expand the sample size to 22 subjects to compensate for the effect size reduction. A power of 83% can be achieved with an effect size of 0.65, alpha value of 2.5% and 22 subjects.

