11.5 Handling of missing data and drop-outs

Unless specified otherwise in each objective, no statistical techniques will be used to impute missing data. If a subject's data are missing for any reason, that subject will not be included in that portion of the analysis. The number of subjects included in each analysis will be reported so that the potential impact of missing data can be assessed.

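### Section 9.2.4 collects no outcome from participants who stop the IMD early, so the Visit 3 secondary comparisons and the questionnaire-based safety outcome rest on those who kept it

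*Protocol*

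**What the plan says.** **Early stop.** Section 9.2.4 reads "After the study concludes the subjects will return the IMD. The follow-up procedure will be the same as for all active test subjects" and goes on to maintenance and fine-tuning of the participant's own aids. It names no questionnaire, test or closing visit. Section 8.5 also promises withdrawn subjects the same follow-up, and explains it as clinic maintenance.

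**Ways off the IMD.** Section 8.3: "If the subject requests to discontinue they can immediately remove the IMD from their ear and return to using their own BTEs". Section 10.1 withdraws a subject whose pain prevents use of the device. Section 7.4 allows withdrawal by the participant or the investigator and keeps back-up participants "to replace those that withdraw or are withdrawn".

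**When IMD outcomes are obtained.** The IMD product questionnaire goes home at Visit 2 and comes back at Visit 3. The SSQ, preference questionnaire and all three WaKo conditions are done at Visit 3 (9.2.2, 9.3.3, and the same in 9.3.6 and 9.3.9). Sections 5.3 and 9.2.3 make the product questionnaire the instrument for unexpected device behaviour.

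**Missing data.** Section 11.5 plans no imputation unless otherwise specified, and states: "If a subject's data are missing for any reason, that subject will not be included in that portion of the analysis". Section 11.4.3 compares product questionnaire answers between devices with a signed-rank test.

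**The concern.** Sections 4.3 and 4.4 ask whether the IMD is inferior in speech or in questionnaire ratings, and whether it behaves unexpectedly. A participant who stops the IMD because of poor sound, artefacts or whistling is directly informative on both, yet is the one from whom no IMD rating is required. If stopping is related to the outcome, the results from those who kept the device look better than the results for everyone fitted with it. Replacement restores the planned number of complete records without restoring this information, and it makes the loss harder to see in the denominator. At stake are the exploratory secondary comparisons, the preference count and the questionnaire part of the safety assessment.

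**Working it through.** **1. The plan's own figures, and whether early stopping touches them.**

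Inputs from section 11.2: "An internal pilot test found an average improvement of 1.54 points (SD 1.63 points", so d = 1.54/1.63 = 0.945, used as 0.94. Phase 3: "would require 11 subjects to show an effect with an alpha value of 2.5%, a power of 80%, and an effect size of 0.94". Phases 1 and 2: "A power of 83% can be achieved with an effect size of 0.65, alpha value of 2.5% and 22 subjects". Section 11.1: "a one-sided test will be used to evaluate the benefit of the IMD in terms of feedback annoyance".

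Power of a one-sided paired t-test = 1 − F(t(0.975, n−1); n−1, d√n), where F is the noncentral t distribution function.

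- n = 11, d = 0.94: noncentrality 0.94 × √11 = 3.118; power 80.2% (n = 10 gives 75.4%). The stated 11 is reproduced.
- n = 22, d = 0.65: noncentrality 0.65 × √22 = 3.049; power 82.8%. The stated 83% is reproduced.

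The live feedback test is done with both devices at Visit 2 (9.2.1, 9.3.2), before the IMD field period, and the ITT set in 11.4.1 takes in participants with primary outcome data. A stop after Visit 2 therefore leaves the primary pair in place and the power unchanged. Only a loss before the Visit 2 test lowers it: two lost and not replaced gives 78.7% (n = 20) or 69.6% (n = 9).

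**2. What is available for someone who stops between Visits 2 and 3.**

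| Item | Obtained | Required if the IMD is stopped early? |
|---|---|---|
| Live feedback, RMD and IMD | Visit 2 | Already in hand |
| RMD product questionnaire | Returned at Visit 2 | Already in hand |
| IMD product questionnaire, with 5.3 questions | Returned at Visit 3 | No route stated |
| SSQ, preference questionnaire | Visit 3 | No route stated |
| WaKo: unaided, RMD, IMD | Visit 3 | No route stated |
| Adverse events, device deficiencies | Throughout (10.1) | Recorded |
| Reason for withdrawal | CRF (12.1.2) | Recorded |

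For the product questionnaire, the missing IMD answer removes the pair from the signed-rank test. For WaKo, both aided scores are missing, so the participant contributes nothing to the mixed logistic model.

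**3. Illustrations only.** The protocol gives no stopping rate, no preference test and no one-sided rule for the questionnaires. All of these are assumed below.

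*Mean Likert difference (IMD − RMD).* If completers average 0 and k of n stoppers would score s, the mean over everyone is k·s/n. With s = −2: 2 of 22 gives −0.18, 3 of 22 gives −0.27, 5 of 22 gives −0.45, and 2 of 11 gives −0.36. With s = −1 these halve. The completer mean stays at 0 throughout.

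*Chance of flagging deterioration.* Simulation of 4,000 runs: completers score −1/0/+1 with probability 0.25/0.5/0.25, one-sided signed-rank test at 2.5%. Completers alone are flagged in about 2% of runs. Including stoppers at −2 gives about 4% (1 of 22), 10% (2 of 22), 17% (3 of 22) and 52% (5 of 22). At −1, 3 of 22 gives only about 8 to 10%.

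*Preference.* With two stoppers counted as not preferring the IMD (p from an assumed one-sided sign test):

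- 22 fitted, no replacement: 15/20 = 75% (p = 0.021) becomes 15/22 = 68% (p = 0.067).
- 22 completers after replacement: 17/22 = 77% (p = 0.008) becomes 17/24 = 71% (p = 0.032).
- Phase 3, no replacement: 8/9 = 89% (p = 0.020) becomes 8/11 = 73% (p = 0.113).

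*Unexpected behaviour.* If two of 22 stop because of it and no completer reports it, the questionnaire shows 0/20 where the true figure is 2/22 = 9%. In Phase 3 it shows 0/9 where the true figure is 2/11 = 18%.

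**4. Use of data already gathered.** Sections 7.4 and 8.3 say data from withdrawn or discontinuing participants are used, and 8.5 plans one section on all recruited subjects and another on completers. Section 10.1 gives the removal of partial data as one purpose of withdrawing a participant for pain. These statements do not agree.

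**The case against.** Several points on the other side stand.

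- A reader might infer that early stoppers drop out of every paired comparison. They do not: the confirmatory comparison keeps them, as step 1 shows.
- A reader might infer that no device-safety information exists for them. Device deficiencies go to the sponsor within 24 hours (10.1.2), and adverse events and the withdrawal reason are recorded. Only the questionnaire component lacks a collection route.
- A reader might infer that their data are deleted as a rule. Sections 7.4, 8.3 and 8.5 say the opposite; only 10.1, for pain, points to removal.
- The back-up list in 7.4, normally at least five, might be read as an expected stopping rate. It is a reserve against any kind of withdrawal, including an ear infection or unreliable responses, and says nothing about how many would stop because of the IMD.
- The field period is about 10 days in experienced users with matched gain, and fine-tuning is available to keep people in the study. Few stoppers is plausible, and with one of 22 the effect is slight.
- Scoring every stopper in the worst category would misattribute some stops. Dome discomfort is an example, since section 6.2.2 says tubing and domes are the same for each IMD style and its comparator.
- A statistical plan is listed as an appendix and may contain sensitivity analyses for dropouts.

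The last point does not close the gap. An analysis plan cannot use scores that were never collected, and collection at early stop is what 9.2.4 exists to fix. The promises in 7.4, 8.3 and 8.5 likewise cover only data that were gathered. A participant might hand back a part-completed home questionnaire with the device, but nothing requires it.

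**Conclusion.** The concern holds for a participant who stops the IMD after Visit 2 and does not attend Visit 3. No section provides for an IMD product questionnaire, SSQ, preference or WaKo result from that participant, so those results come only from people who kept the device. The likely direction is towards no deterioration and, for preference, towards the IMD, provided that some stops are caused by the IMD. The size cannot be derived from the protocol; the figures above rest on assumed numbers of stoppers, assumed scores and tests the protocol does not state. The outcomes concerned are exploratory apart from the questionnaire-based safety outcome. The documents do not support extending the point to the primary analysis, its sample size or the whole of the safety record. The conflict between 10.1 and sections 7.4, 8.3 and 8.5 is a separate textual fault and needs resolving in any case. A cheap improvement to data collection is warranted; a change of main analysis is not.

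**What to change.** - **9.2.4:** ask every participant who stops the IMD after Visit 2 to complete, if willing, the IMD product questionnaire for the days worn and the preference questionnaire when handing back the device.
- **11.4.3 and 11.5:** include these scores in the RMD–IMD comparison. Report stoppers and their reasons beside completers, and state that replacements do not take stoppers out of the denominator.
- **Sensitivity analysis only:** count stops attributed to the IMD against it. This should not be the main analysis.
- **10.1 against 7.4, 8.3 and 8.5:** reconcile the statements on whether partial data from withdrawn participants are kept and used.

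Cost: wording in these sections and a few minutes per stopper. The forms exist and participants are already asked to return the device. Ratings after short wear will be noisier, and some who withdraw will decline. The sample size does not change.
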